## 9.7. Data Analysis

The labeling updates due to the Article 20 procedure pose distinct challenges for the long-term safety study in atopic dermatitis (AD). First, patients treated with upadacitinib will be expected to differ from other select systemic treatments in baseline risk factors for major cardiovascular events (MACE), malignancy and/or venous thromboembolic events (VTE), based on the updated section 4.4 (Special warnings and precautions for use) of the RINVOQ Summary of Product Characteristics (SmPC). Second, high risk patients treated with upadacitinib will likely be those with “no suitable treatment alternatives” and be more likely to have failed other therapies, not responded to the lower dose of upadacitinib, and have higher disease burden. Third, the anticipated lower incidence of safety outcomes in low-risk patients raises feasibility concerns, particularly as these relate to precision requirements for comparative analyses.

To address these challenges, assessment of comparability of users of upadacitinib and other select systemic treatments for AD will be conducted through in-depth assessments of treatment pattern utilization and patient disposition at baseline (see Section 9.7.1).

### 9.7.1. Descriptive Analysis

All descriptive statistics will be presented separately for Sweden and Denmark. Mean (standard deviation [SD]) and median (25th percentile, 75th percentile) will be used as descriptive statistics for continuous variables and counts and proportions for categorical variables.

Descriptive analyses will be conducted to characterize the users and the real-world utilization of upadacitinib and other select systemic AD treatments to assess suitability of treatment groups as potential comparators to the upadacitinib cohort. These descriptive analyses will provide guidance on potential comparators and feasibility of comparing incidence rates across treatment cohorts.

Drug utilization and individual baseline characteristics (e.g.; demographics, comorbidities, concomitant treatments, treatment experience, healthcare utilization) will be summarized for upadacitinib and select systemic AD treatments, separately for each country, by dose (upadacitinib), age group at initiation, relevant risk factors (e.g., malignancy, VTE, and MACE), and disease history as listed in the secondary objectives (moderate hepatic impairment, hepatitis B & C, severe renal impairment).

PS will be generated for upadacitinib users and other select systemic AD treatments users [55-57]. The distribution/overlap of propensity scores will be examined to assess the balance across cohorts. The SMD will be used to assess comparability across treatment groups if needed.

Person-years at risk and the number of safety outcomes for upadacitinib will be reported overall and across risk factor strata, crude incidence rates for upadacitinib will be presented. If suitable/comparable treatment cohorts can be identified, crude incidence rates for all safety outcomes will be provided for other select systemic AD treatments, as well.

Descriptive analyses will be performed in the interim report and the final report.

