To reduce inflammation in the skin, either pimecrolimus or tacrolimus can be used for topical treatment. They are calcineurin inhibitors that affect inflammatory dendritic epidermal cells and are recommended as second line treatment due to safety reasons [2]. When using anti-inflammatory treatments, combined therapy with emollients should be used. In rare instances oral corticosteroids may be used for the treatment of exacerbation of AD [2]. For very severe cases of AD, cyclosporin A may be used [2]; however, there are side effects including renal toxicity that may lead to hypertension and renal impairment. Another drug sometimes used for severe AD is azathioprine. However, side effects include myelo-suppression, hepatotoxicity, gastrointestinal disturbances, increased risk of infections and possibly skin cancer.

More recently, subcutaneous, oral and topic biologic drugs have been introduced for clinical use in AD. In 2017, the monoclonal antibody dupilumab was approved in the US and EU for adults with moderate to severe AD. Dupilumab binds to interleukin-4 (IL-4) receptors which are involved in signaling pathways relevant for the development of AD [16]. Abrocitinib was approved for adults with moderate to severe AD in the EU in December 2021. Moreover, additional drugs may come to be introduced to the market (e.g., crisaborole, nemolizumab) [17, 18].

Upadacitinib is an oral selective and reversible inhibitor of JAK1. Upadacitinib doses of 15 mg and 30 mg are approved to be used in the EU for treatment of adults with moderate to severe AD. Upadacitinib 15 mg is approved to be used in the EU for treatment of adolescents with moderate to severe AD who weigh 30 kg or over. Following the procedure under Article 20 of Regulation (EC) No 726/2004 (concluded 10 March 2023), upadacitinib recommended use and doses have been changed. Upadacitinib 15 mg is approved to be used in the EU for treatment of elderly patients  $\geq 65$  years of age or patients with risk factors for malignancy, major adverse cardiovascular events (MACE) or venous thromboembolic events (VTEs). In addition, upadacitinib should only be used, if no suitable alternatives are available, in patients 65 years of age or older, in patients with history of atherosclerotic cardiovascular disease or other cardiovascular risk factors and in patients with malignancy risk factors.

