## 9. Research Methods

### 9.1. Study Design

The study is based on data from the nationwide health and administrative registers from Denmark and Sweden, covering country populations of approximately 5.8 million and 10.2 million people, respectively. It is a longitudinal, non-interventional, population-based, register-based cohort study of adolescents and adults with AD exposed to upadacitinib or other select systemic AD treatments, identified in the Danish and Swedish nationwide registers.

Importantly, labelling changes following Article 20 procedure are likely to result in substantial differences in baseline characteristics of patients initiating upadacitinib and those initiating other systemic treatments. Therefore, initial in-depth descriptive analyses will be conducted to assess comparability across treatment cohorts and inform the design (including selection of suitable comparator/s) of subsequent analyses.

The select systemic AD treatments (including biosimilars) evaluated as potential comparator treatments in the study are:

- Azathioprine
- Ciclosporin
- Dupilumab
- Methotrexate
- Mycophenolate mofetil

ATC codes and procedure codes for the comparator treatments are listed in Annex 3. Additional Information, [Table 3.2](#). Additional upcoming marketed AD treatments may become relevant as comparator treatments as the study progresses. Therefore, the list may be extended to cover

other available and approved AD treatments in Sweden and Denmark during the study period. Final codes and definitions will be specified in the Statistical Analysis Plan (SAP) before data extraction for interim analysis and final analysis.

A *new user*, active comparator design will be used to address the objectives of the study. *New user* is defined as not having used that specific drug substance in the year (12 months, 365 days) before the first eligible treatment.

The first dispensed prescription/administration date of upadacitinib or one of the comparator treatments within the study period (see definition in Section 9.2.2. ), will be defined as the *index date*.

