### 9.2.2. Study Period

The *study period* ranges from first authorization date of upadacitinib for the treatment of AD in Denmark and Sweden (23 August 2021) until 31 December 2031.

Individuals initiating one of the treatments under study will be included through the whole *study period*. To allow for at least 5 years follow-up time for malignancy excluding NMSC and NMSC, for these outcomes the population will be restricted to individuals included up until 31 December 2026.

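### The comparability assessment spans the 10 March 2023 label change without separating patients who started before and after it, which can dilute the imbalance it is meant to detect

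*Protocol*

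**What the plan says.** Section 9.1 states that "labelling changes following Article 20 procedure are likely to result in substantial differences in baseline characteristics of patients initiating upadacitinib" compared with patients starting other systemic treatments. It therefore makes the initial descriptive analyses the basis for choosing comparators and designing later analyses. Section 9.7 adds that "patients treated with upadacitinib will be expected to differ from other select systemic treatments in baseline risk factors" for MACE, malignancy and VTE. It also expects high-risk upadacitinib users to have more treatment failure and a higher disease burden. Section 7 dates the conclusion of the Article 20 procedure to 10 March 2023.

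Section 9.2.2 sets the calendar window, which "ranges from first authorization date of upadacitinib for the treatment of AD in Denmark and Sweden (23 August 2021) until 31 December 2031", and says that "Individuals initiating one of the treatments under study will be included through the whole" of that window. For malignancy and NMSC, "for these outcomes the population will be restricted to individuals included up until 31 December 2026".

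In section 9.7.1, drug utilization and baseline characteristics "will be summarized for upadacitinib and select systemic AD treatments, separately for each country, by dose (upadacitinib), age group at initiation, relevant risk factors" and the disease histories of the secondary objectives. The subgroups in 9.7.2.1 are dose, age group, risk factors and disease history. Table 1 lists no calendar date or period of initiation. SMDs are to be used if needed, with no threshold. The descriptive analyses go into both the interim and the final report; the comparison goes into the final report only.

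**The concern.** Comparability is the first primary objective, and it is there because the label changed partway through accrual. The plan nevertheless describes the cohort without dividing it at that change. If channelling appears mainly among later starters, a pooled SMD or overlap plot averages it with starters to whom the new label did not apply. A comparator could then look more suitable for current use than it is.

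Upadacitinib incidence is a primary objective even if no comparator is found. It would average two populations that the protocol itself expects to differ. Earlier starters also have longer follow-up, so they weigh more in the rates than in the baseline tables.

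**Working it through.** The plan states no figure on this point and its study-size figures are blacked out, so there is nothing to reproduce. The check uses the plan's dates plus stated assumptions.

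**Dates (sections 7 and 9.2.2)**
- 23 August 2021 to 10 March 2023: 564 days (1.54 years).
- 23 August 2021 to 31 December 2026: 1,956 days (5.36 years). This is the malignancy/NMSC entry window and, with data to December 2026, the interim window.
- 23 August 2021 to 31 December 2031: 3,782 days (10.35 years).

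**Assumptions.** Accrual is either uniform or a linear ramp from zero. Nobody is censored before the data cut. Malignancy carries the 12-month lag from section 9.3.2.

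**Share of entrants.** Let x be the pre-change fraction of the entry window. The share is x under uniform accrual and x² under the ramp.
- To December 2026: x = 564/1,956 = 28.8%; x² = 8.3%.
- To December 2031: x = 564/3,782 = 14.9%; x² = 2.2%.

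**Share of person-time.** Where entry and follow-up end together, the share is 1 − (1 − x)² under uniform accrual and 3x² − 2x³ under the ramp.
- Interim, outcomes without a lag: 1 − 0.712² = 49%; ramp 20%.
- Final report, outcomes other than malignancy and NMSC: 1 − 0.851² = 27.6%; ramp 6.0%.

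For malignancy in the final report, entry stops at T = 5.36 years, follow-up ends at 10.35 years and the first year is dropped. Each entrant at time t then contributes 9.35 − t years. With a = 1.54:
- Uniform: (9.35a − a²/2)/(9.35T − T²/2) = 37%.
- Ramp: (9.35a²/2 − a³/3)/(9.35T²/2 − T³/3) = 12%.

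**Dilution, with assumed prevalences.** Suppose a risk factor is present in 25% of both groups before the change, and in 20% of upadacitinib starters against 25% of comparator starters after it. SMD = (p1 − p0)/√{[p1(1 − p1) + p0(1 − p0)]/2}. After the change this is −0.05/√[(0.16 + 0.1875)/2] = −0.12. Before the change it is 0. Pooled, with w the pre-change share of upadacitinib starters, p1 = 0.25w + 0.20(1 − w):

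| w | pooled p1 | pooled SMD |
|---|---|---|
| 28.8% | 0.214 | −0.084 |
| 14.9% | 0.207 | −0.10 |
| 8.3% | 0.204 | −0.11 |
| 2.2% | 0.201 | −0.12 |

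Against an assumed threshold of 0.1 the imbalance is hidden in the first row, borderline in the second, and visible in the last two.

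**Cancellation.** For opposite imbalances to cancel exactly, the pre-change excess must be (1 − w)/w times the post-change deficit: about 2.5 times at 28.8%, 5.7 times at 14.9%, 11 times at 8.3% and 44 times at 2.2%.

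**The case against.** **The existing strata cover the label's routes.** The change acts through age, dose and malignancy, MACE and VTE risk factors, and the protocol tabulates by all of these. That covers measured channelling in part. It does not separate early from late starters within a stratum, and section 9.7 expects treatment failure and disease burden to differ among high-risk users. Section 9.9 concedes that score-based severity is not recorded, so the residual shift is one the other variables may not show.

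**This belongs in the SAP, and parts are blacked out.** The propensity-score covariates, the choice of method and the sensitivity-analysis details are left open, and text in section 9.7.2 is not readable. Adjustment for period cannot be ruled out, and its exact form is properly a SAP matter. The strata of the comparability assessment, though, are written and readable here, without period. The abstract speaks of comparability after the referral procedure, but no rule limits or splits the assessment accordingly.

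**A stronger reading.** A reader might infer that imbalances before and after the change run in opposite directions and cancel, so that an unsuitable comparator passes. The documents do not support this. They describe only the difference expected under the updated label and give no direction or size for any earlier imbalance. Cancellation also needs a sizeable pre-change share or a large earlier excess. If a measured factor did balance when pooled, crude confounding by it would largely cancel too, apart from the longer follow-up of early starters. Nor is it true that a pooled propensity score cannot handle a change over time, since it can include period and interaction terms.

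**The interim shares overstate the effect on the comparison.** This stands. Hazard ratios come only in the final report, where the pre-change share is smaller for most outcomes.

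**Conclusion.** The point holds as one of mixing and possible dilution. Entry crosses a change that the protocol expects to alter the treated population, and the readable strata, subgroups and baseline variables do not mark it. The effect is largest in the interim report and the malignancy/NMSC cohort. It is smaller, and under a ramp slight, for the other ten outcomes in the final report. The shares rest on assumed accrual shapes, and the SMD example on assumed prevalences and an assumed 0.1 threshold, so whether an imbalance is actually masked depends on uptake. Cancellation remains only a possibility. This is a cheap improvement to the first primary objective, not a must-fix.

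**What to change.** In section 9.7.1, add initiation period (before versus from 10 March 2023) as a stratum for baseline characteristics, propensity-score overlap, SMDs and upadacitinib incidence rates. State that the post-change results will be taken into account when comparator suitability is judged.

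In section 9.7.2, include initiation period in the propensity score or stratify the Cox model by it, and add a sensitivity analysis restricted to post-change starters. Period-specific hazard ratios can be optional where event counts allow. Requiring them, or separate propensity models by period, as main analyses would split outcomes for which section 9.7 already raises precision concerns.

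The cost is wording and extra table columns, because index dates are already held. The drawback is smaller cells in the added columns. The change should be made before the comparability assessment is run, since comparator selection follows from it.

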### 9.7.2. Comparative Analysis

[REDACTED] analyses will be performed to compare upadacitinib and comparator treatments in the final report.

Comparisons of rates of safety outcomes between upadacitinib and comparator cohorts will be made with Cox proportional hazard regression models using appropriate strategies such as IPTW, PS matching/ stratification/ adjustments or others to achieve comparable balance across cohorts.

[Table 7](#) below specifies the exposure definitions that will be used as time at risk for each outcome.

With the ITT exposure definition, individuals will be considered exposed to the first eligible treatment received until the end of follow-up while with the modified ITT individuals will be considered exposed to the first eligible treatment received and censored at treatment switching. With both ITT and modified ITT, Cox proportional hazards regression models with treatment group (upadacitinib, comparator) as exposure will be performed. For malignancy, exposure time and time to event will start to be counted from the lag-time (for main analysis 12 months) from index date.

With the time-varying exposure definition individuals may change exposure status when starting different treatments, and thus the treatment covariate is time-varying. Cox proportional hazards regression models with treatment group (upadacitinib, comparator, unexposed time, concomitant use/switch) as covariate will be performed. The time scale in the models will be time since start of the treatment group, i.e., time since beginning of the exposure to the specific treatment group (upadacitinib, comparator, unexposed time, concomitant use/switch).

The hazard ratio (HR) and 95% confidence interval (CI) will be reported from the Cox models. Kaplan-Meier curves for all outcomes will also be reported. In addition, 5-years overall survival rate will be presented for malignancy excluding NMSC, NMSC, MACE and all-cause mortality as well as 5-years event-free survival rates for malignancy excluding NMSC, NMSC and MACE.

Analyses will be performed based on pooled individual data, unless legal barriers towards transfer of individual data make it impossible, in which case meta-analyses of aggregated data will be performed instead. Methods for meta-analysis will be described in the SAP and the barriers for data pooling will be assessed in connection with the interim report.

**Table 7 Exposure definition per outcome**

Outcome	Exposure definition
Malignancy (excluding NMSC), malignancy by type	
NMSC	
MACE	
All-cause mortality	
VTE	
Serious (in-patient) infections (incl. opportunistic infections)	
HZ	
EH/KVE	
Active TB	
GI perforations	
DILI	
Fractures	

**9.7.2.1. Sensitivity Analysis and Subgroup Analysis**

Sensitivity analyses for all safety outcomes will be performed among individuals in the study population with no prior use of any of the other systemic AD treatments within 12 months from *index date*. Sensitivity analyses with 0- and 6-months lag time for malignancy outcomes will be conducted.

In addition, subgroup analyses will be performed by upadacitinib dose, age group, relevant risk factors (e.g., malignancy, VTE, and MACE) and disease histories as listed in the secondary objectives.

Details on the sensitivity and subgroup analyses for all safety outcomes will be described in the SAP.

### **9.7.3. Missing data**

Within each data source, if information on a particular variable is available, individuals will be assumed not to have the factor if there is no evidence for its presence (i.e., values for variables used in a given data source will not be considered missing). The only exception to this principle will be in the situation where "missing" is one of the possible values recorded for the variable, in which case the value as listed within the data source will be retained in the analysis as one of the possible values (e.g., a variable can be "yes" "no" or "missing"). Missing data will not be imputed but treated as missing.

### **9.8. Quality Control**

Data storage, management and analyses will be conducted according to each institution's standard procedures. At a minimum, the statistical analysis will be supervised by a senior statistician and all study documents (protocol, report, publications) will be reviewed by the entire research team. A senior epidemiologist in each institution will review the report before submission to the sponsor. Clinical expertise is available for appropriate interpretation of results. At the start of the project, a regular communication plan will be established (via e-mail and regular teleconferences), and internal timelines will be established to allow review and quality control before submitting each deliverable. Each institution will also follow its internal quality control procedures and will ensure the necessary compliance with local data protection, storage and archiving, and patient privacy laws and regulations and will obtain all permission necessary to conduct this study.

### **9.9. Limitations of the Research Methods**

Some information is not collected in national registers including score-based AD disease severity and patient reported outcomes. Individuals only diagnosed with AD in primary care will not be included, and diagnostic information for conditions only seen in primary care will also be missing. The ability to assess and address bias will be detailed in the selection of comparison treatments and in the analytic approach. Confounders will be identified and adjusted for and the potential for residual confounding will be considered, and any relevant sensitivity analyses will be proposed. The role of unmeasured confounding and its influence on the study results will be discussed in the reports.

### **9.10. Other Aspects**

Not applicable.

## **10. Protection of Human Subjects**

The study is based on register data only and will not require informed consent [58]. In Denmark, no Institutional Review Board (IRB)/Independent Ethics Committee (IEC) approval is required for studies based on data from routine registries. An approval from the Danish Data Protection Agency, required for all studies, will be obtained. In Sweden, an IEC approval will be obtained from the Swedish Ethical Review Authority. Approval from the Swedish Data Protection Agency is

not required. The register holders will pseudonymize the linked individual-level data by replacing the PIN with a project specific unique number. Country-specific data will be kept in secure servers at Statistics Denmark and at KI, and only members of the investigator teams will have access to the data in their respective countries. The investigators will comply with the EU General Data Protection Regulation (GDPR) and its implementation in the national legislations by May 2018 in the processing of personal data. Additionally, we will adhere to commonly accepted research practices, including those described in the following guidance documents: European Network of Centres for Pharmacoepidemiology and Pharmacovigilance (ENCePP) Guide on Methodological Standards in Pharmacoepidemiology, ENCePP Code of conduct, Guidelines for Good Pharmacoepidemiology Practices issued by the International Society for Pharmacoepidemiology, FDA Guidance for Industry: Good Pharmacovigilance and Pharmacoepidemiologic Assessment, and FDA Guidance for Industry and FDA Staff: Best Practices for Conducting and Reporting of Pharmacoepidemiologic Safety Studies Using Electronic Healthcare Data Sets.

AbbVie will get access to the aggregated results, but not the individual-level data used in the study.

